3 INVESTIGATIONAL PLAN

3.1 General

Study size: 27 subjects (up to 150 subjects screened to randomize a total of 27 subjects)

Study duration: 1 year

Study duration of individual subjects (not including screening): 90 days

Sex distribution: males and females

Age range: 18 to 60 years

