3.3 Definitions for the Purpose of this Study

Definitions for the Purpose of this Study:

Enrolled

For the purpose of collecting data and samples and reporting adverse events (AEs), a subject will be considered enrolled beginning from when the informed consent form is signed until the subject is considered “screen failure”, “discontinued”, or “completed”.

Randomized

Subjects are considered randomized when they meet all of the following criteria:

- Enrolled (as defined above)
- Confirmation that the inclusion and exclusion criteria are met
- Randomization number is assigned

Screen Failures

Subjects are considered screen failures when they meet one or more of the following criteria after signing consent:

- Screening tests reveal that the subject is ineligible
- Subject withdraws consent before being randomized

Discontinued

Subjects are considered discontinued when they meet one or more of the following criteria:

- Subject withdraws consent after being randomized and prior to the completion of Day 90 (see Section 4.6)
- Subject is withdrawn after enrollment by Investigator (see Section 4.7) including lost to follow-up

Completed

Subjects are considered completed when they are followed through Study Day 90 and complete the final study follow-up visit (Study Day 90).

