6.2 Screening

Screening evaluations may be done up to 28 days before Day 0.

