6.3 Detailed Description of Assessments

6.3.1 Schedule of Assessments

The schedule of assessments is described in Table 3. The day when the subject is randomized is denoted as Study Day 0, the first day after enrollment is Study Day 1, etc.

Table 4: Schedule of Assessments

	Screen	Baseline							
Day +/- Window	-28 to -1	-1 to 0	1	2	3 (+1)	7 ± 1	21 ± 2	42 ± 3	90 ± 7
Evaluation/Procedure		Prior to infusion							
ELIGIBILITY									
Informed consent	X								
Demographics	X								
Medical history	X								
RANDOMIZATION/ STUDY DRUG									
Randomize subject		X							
Study drug administration		X							
STUDY PROCEDURES									
Assess Symptoms		X	X	X	X	X	X	X	X
Vital signs	X	X	X	X	X	X	X	X	X
Review of concomitant medications	X	X	X	X	X	X	X	X	X
Physical exam	X	if needed to assess AEs							
ECG	X								
Adverse events		X	X	X	X	X	X	X	X
SAFETY LABORATORY ^a									
CBC	X	X		X	X	X		X	X
PT/PTT	X	X		X	X	X		X	X
Reticulocyte Count	X	X		X	X	X		X	X
Chemistry Panel	X	X		X	X	X		X	
Urinalysis	X	X		X	X	X		X	
Quantitative Immunoglobulin	X	X		X	X	X	X	X	X
Rheumatoid factor	X	X		X	X	X	X	X	X
Urine biomarkers	X	X		X	X	X		X	
Pregnancy test (urine or serum)	X	X							
UDS	X	X							
REFERENCE PROCEDURE									
Stored serum for pharmacokinetics		X ^b	X	X	X	X	X	X	X
Stored serum for immunogenicity ^c			X			X	X	X	X

Notes. a) Elements of each panel are listed in Section 7.1.1

b) PK sample on Day 0 includes baseline (pre-infusion), 1 hour (+/- 15 min) after the end of the infusion, and 6 hours (+/- 30 min) after the end of the infusion.

c) Serum will be collected for immunogenicity assessment for subjects at the time of an AE suggestive of hypersensitivity reaction (including serum sickness) even if the AE does not coincide with a visit in which immunogenicity assessment is planned.

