11.7 Pausing Rules

If any of the following criteria are met at any time the study will be paused to further enrollment until assessed by the sponsor medical monitor:

- Any SAE as defined in Section 10.3 that can be possibly, probably, or definitively attributed to the study drug
- Three or more subjects in the same cohort experiencing the same Grade 2 or higher adverse effect that can be possibly, probably, or definitively attributed to the study drug
- Two or more subjects develop the same or clinically similar Grade 3 AE or laboratory abnormality
- Two or more subjects develop a serum creatinine \geq Grade 2 toxicity (≥ 1.8 mg/dL)
- Two or more subjects develop \geq 1.5-fold increase in serum creatinine level from baseline
- Two or more subjects develop GFR <70 mL/min, irrespective if serum creatinine is normal range or Grade 1
- Two or more subjects develop a serum creatinine \geq Grade 2 toxicity in PT and/or PTT (i.e. one grade 2 PT and one grade 2 PTT would meet this pausing rule)

The sponsor medical monitor can request information needed (such as a listing of graded AEs) and unblinded randomization scheme (directly from the site investigational pharmacy group) to evaluate the data. For individual subject unblinding, the site will follow their unblinding procedures per SOP-AUSCLN-506. The sponsor medical monitor will ultimately make the decision to either resume the study or stop the study.

If the trial is stopped due to unacceptable adverse events or stopping criteria, the IRB will be notified.

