11.8 Dose Escalation Rules

When the results from the Day 7 visit for the last subject in a cohort (e.g., Cohort 1) are available safety parameters will be analyzed to determine the overall safety of that dose-level (e.g., 1 mg/kg). If any of the following criteria are met, the corresponding dose-level is not considered “acceptably safe”, and the study will not proceed to the next higher dose group (as the review is blinded, this will be across treatment arms).

- Any SAE that can be possibly, probably, or definitively attributed to the study drug
- Any immediate hypersensitivity or cytokine storm events
- Two or more subjects with asymptomatic positive anti-IgG (rheumatoid factor)
- One or more subjects with positive anti-IgG (rheumatoid factor) with associated rheumatologic symptoms (i.e. arthralgia, myalgia, etc.)
- Two or more subjects across all cohorts experience the same Grade 3 or higher adverse effect that can be possibly, probably, or definitively attributed to the study drug

- Three of the first 10 subjects (30%) experience the same grade 2 or higher adverse effect that can be possibly, probably, or definitively attributed to the study drug or any time thereafter 30% of enrolled subjects have the same grade 2 or higher 'related' AE.
- Two or more subjects across cohorts develop a serum creatinine \geq Grade 2 toxicity (≥ 1.8 mg/dL) or doubled from baseline (whichever is lower)

If any of the above criteria are met at any time, then the medical monitor will evaluate unblinded study data and make a determination about continuation of the study and/or amendment of the protocol.

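### The related Grade 2 or higher criterion in section 11.8 uses a denominator ('enrolled') that the protocol does not define as dosed, and by pooling cohorts it seldom bars escalation to 50 mg/kg for an AE that first appears at 25 mg/kg

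*Protocol*

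**What the plan says.** Section 11.8 reviews each cohort once the Day 7 results of its last subject are available: "safety parameters will be analyzed to determine the overall safety of that dose-level". One criterion concerns the same related AE of Grade 2 or higher. It is met by 3 of the first 10 subjects, or if at "any time thereafter 30% of enrolled subjects have the same grade 2 or higher" related event. The review is blinded and pools the arms. A met criterion means that the next dose is not given by default. A closing sentence, beginning "If any of the above criteria are met at any time", sends the matter to the medical monitor, who sees unblinded data and decides on continuation.

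Section 3.3 says that "a subject will be considered enrolled beginning from when the informed consent form is signed", and ends that status at screen failure, discontinuation or completion. It defines 'randomized' separately. Section 6.3.1 uses the word differently: after making the day of randomization Day 0, it says "the first day after enrollment is Study Day 1".

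Section 11.7 has a per-cohort rule: "Three or more subjects in the same cohort experiencing the same Grade 2 or higher adverse effect", if related, pauses further enrolment until the sponsor medical monitor has assessed it. The monitor may then resume or stop the study.

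**The concern.** There are two separate points.

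**Denominator.** A percentage rule for drug-related events should count people who received the infusion. With the section 3.3 definition it also counts consented candidates, and it loses subjects who have completed or discontinued. Candidates for the next cohort may well be waiting at a review, since "Screening evaluations may be done up to 28 days before Day 0" and section 3.1 allows "up to 150 subjects screened to randomize a total of 27 subjects". The number of cases that blocks escalation would then depend on recruitment.

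**Pooling.** The review judges one dose level, but the percentage runs over all cohorts. Subject 10 is the first subject of Cohort 3, so the 'first 10' clause sees at most one person at 25 mg/kg. For an AE that emerges at that dose, the nine earlier subjects dilute the percentage. The criterion is then harder to meet at the Cohort 3 review than at the Cohort 2 review, just before the highest dose.

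**Working it through.** **Inputs.** Table 1 gives SAB-176 + saline of 2+1, 4+2, 6+2 and 8+2, that is 3, 6, 8 and 10 subjects, cumulatively 3, 9, 17 and 27. This reproduces the stated total of 27, and 3/10 reproduces the stated 30%.

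**Cases needed** = 0.30 × n, rounded up:

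| n | 10 | 11–13 | 14–16 | 17–20 | 21 | 27 |
|---|---|---|---|---|---|---|
| cases | 3 | 4 | 5 | 6 | 7 | 9 |

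**Denominator as defined, at the Cohort 3 review (17 dosed).** The numbers of waiting candidates are assumptions; the protocol gives none.

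- 4 consented Cohort 4 candidates: n = 21, 7 cases needed, more than the 6 SAB-176 recipients in Cohort 3.
- 10 candidates: n = 27, 9 cases needed, more than all 8 Cohort 3 subjects.
- All three Cohort 1 subjects already past Day 90 and nobody waiting: n = 14, 5 cases suffice. This needs slow conduct. On the fastest section 3.2 schedule (Cohort 1 on days 1, 3 and 5; Cohort 2 on days 13–19; Cohort 3 on days 27–34) the last Day 7 visit falls on day 41.

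**Dosed subjects, no earlier cases, AE only in Cohort 3 SAB-176 recipients.** A single check at 17 needs 6 cases, because 5/17 = 29.4% falls short. For a running check, place k cases among dosing positions 10 to 17, all orderings equally likely, each case known before the next infusion:

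- k = 3: 0 of 56 orderings meet the criterion.
- k = 4: 1 of 70 (the first four of the cohort, 4/13 = 30.8%).
- k = 5: 22 of 56 (39%).
- k = 6: all.

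**With earlier cases of the same AE, running check.**

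- One earlier case: 3 new cases meet it in 4 of 56 orderings (7%), 4 new in 39 of 70 (56%), 5 new always.
- Two earlier cases: 3 new cases meet it in 44 of 56 (79%), 4 new always.
- On a single check at 17, one earlier case leaves 5 new cases needed, and two leave 4.

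**Probabilities.** Let p be the assumed true rate in the SAB-176 recipients of the cohort under review. For Cohort 3 the running probability is the sum over k of C(6,k) p^k (1−p)^(6−k) × (fraction of orderings). At p = 0.5: 15/64 × 1/70 + 6/64 × 22/56 + 1/64 = 0.003 + 0.037 + 0.016 = 0.056.

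| Rule | p = 50% | 70% | 90% |
|---|---|---|---|
| Cohort 2 review, P(Bin(4,p) ≥ 3) | 31% | 65% | 95% |
| Cohort 3, running check | 5.6% | 24% | 67% |
| Cohort 3, single check at 17, p^6 | 1.6% | 12% | 53% |
| Cohort 3, running, assumed 5% rate in the other 11 dosed subjects | 18% | 42% | 79% |
| Cohort 3, running, assumed 10% rate in those 11 | 30% | 56% | 87% |
| Same-cohort count of 3, P(Bin(6,p) ≥ 3) | 66% | 93% | 99.9% |

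The two background rows are conditional on fewer than 3 cases in the first 9 subjects. The other rows assume no background cases.

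**The case against.** **On 'enrolled'.** The section 3.3 definition opens by limiting itself to data and sample collection and AE reporting. Elsewhere the protocol uses enrolment for randomization or dosing: section 6.3.1 does, and the Table 2 footnote speaks of enrolment where the matching section 3.2 bullet speaks of dosing. The neighbouring clause in 11.8 counts the first 10 subjects, and a drug-related AE presupposes an infusion. This stands as evidence of intent. It does not remove the defect, because 11.8 uses a term that the protocol defines otherwise.

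**On pooling.** A per-cohort pause in 11.7 alongside a cumulative rule in 11.8 is a coherent pair. Three same-cohort cases stop enrolment until the monitor acts, and a core committee must authorise advancement (section 11.4). The first three subjects of Cohorts 2 to 4 are reviewed before further dosing. Related SAEs, hypersensitivity or cytokine storm, repeated related Grade 3 events, creatinine and rheumatoid factor findings each bar escalation separately. What remains is mainly non-serious Grade 2 events outside those categories. All of this stands and keeps the point minor.

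**Stronger readings that the protocol does not support.**

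- A reader might infer that 3 or 4 cases at 25 mg/kg rarely or never bar escalation, whatever came before. That holds only with no earlier cases of that AE.
- A reader might infer that waiting candidates make the criterion impossible to meet. With 4 candidates it is out of reach of the 6 SAB-176 recipients only if those candidates consented before the sixth case was known. Otherwise 6/17 has already met a running check.
- A reader might infer that escalation could proceed unreviewed. Section 11.7 rules that out at 3 related same-cohort cases.
- Section 3.2 enlarges cohorts to detect toxicity. This criterion governs the response to events and does not reduce detection.

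**Conclusion.** The concern holds in a limited form, and its severity is minor. As worded, the 30% applies to a population that section 3.3 does not equate with dosed subjects, and it can err in either direction: 7 or 9 cases needed with 4 or 10 waiting candidates, 5 if Cohort 1 has completed, against 6 on the 17 dosed. On dosed subjects, an AE with no earlier cases that emerges in SAB-176 recipients at 25 mg/kg meets the criterion never with 3 cases, in 1 of 70 orderings with 4, and in 39% with 5 (running check). A single check at 17 needs all 6. Earlier or background cases raise the sensitivity considerably. The consequence is confined to the default: after an 11.7 pause the monitor may resume and the committee may advance, whereas a met 11.8 criterion would block escalation to 50 mg/kg unless the monitor determined otherwise. The probabilities rest on assumed AE rates, equally likely orderings and prompt knowledge of each AE, and they leave out the other 11.8 stops.

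**What to change.** Main change: in the section 11.8 criterion, replace 'enrolled' with 'dosed'. This costs nothing beyond the wording amendment.

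Second change: beside the pooled 30%, add '3 or more subjects in the current cohort with the same related Grade 2 or higher AE', which reuses the 11.7 threshold. Among escalation decisions it alters only 25 to 50 mg/kg, because in Cohorts 1 and 2 the 'first 10' clause already acts at 3 cases. Through the closing 'at any time' sentence it would also prompt a medical monitor determination in Cohort 4.

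No extra subjects or procedures are needed. The downside is a few more chance triggers. At an assumed background rate of 5% or 10% for one such AE, 3 or more cases occur with probability 0.6% or 3.8% in Cohort 3 (P(Bin(8,q) ≥ 3)) and 1.2% or 7.0% in Cohort 4 (P(Bin(10,q) ≥ 3)). All of these would already pause the study under 11.7.

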11.9 Study Endpoints

11.9.1 Primary Endpoint

- Type and frequency of AEs experienced by subjects receiving SAB-176 at escalating dose-levels, as compared to placebo

11.9.2 Secondary Endpoints

- Pharmacokinetic profile of intravenously administered SAB-176 in healthy adults
- Hemagglutination Inhibition (HAI)
- Microneutralization (MN)
- Frequency and concentrations of antibodies caused by SAB-176, as measured by:
 - Anti-IgG antibodies using rheumatoid factor
 - Anti-SAB-176

12 ETHICS/PROTECTION OF HUMAN SUBJECTS

12.1 Informed Consent Process

Informed consent is a process where information is presented to enable persons to voluntarily decide whether or not to participate as a research subject. It is an on-going conversation between the human research subject and the researchers about the essential information about the study, which begins before consent is given and continues until the end of the subject's involvement in the research. Discussions of essential information about the research will include the study's purpose, duration, experimental procedures, alternatives, risks, and benefits. Subjects will have the opportunity to ask questions and have their questions answered.

The participants will sign the informed consent document prior to any procedures being done specifically for the study. The participants may withdraw consent at any time throughout the course of the trial. A copy of the informed consent document will be given to the participants for their records. The researcher will document the signing of the consent form in the subject's medical record. The rights and welfare of the participants will be protected by emphasizing to them that the quality of their medical care will not be adversely affected if they decline to participate in this study.

12.2 Subject Confidentiality

All records will be kept confidential to the extent provided by federal, state and local law. Study monitors and other authorized representatives of the Sponsor may inspect all documents and

records required to be maintained by the Investigator, including but not limited to, medical records. Records will be kept locked and all computer entry and networking programs will be done with coded numbers only. Clinical information will not be released without written permission of the subject, except as necessary for monitoring by IRB, the FDA, or the sponsor's designee.

13 DATA MANAGEMENT AND MONITORING

13.1 Data Management Responsibilities

The Investigator is responsible for assuring that the data collected is complete, accurate, and recorded in a timely manner. Source documentation (the point of initial recording of information) should support the data collected in the electronic data system, and must be signed and dated by the person recording and/or reviewing the data. All data should be reviewed by the Investigator and signed as required electronic signature.

13.2 Data Capture Methods

Study data will be collected at the study site and maintained in an electronic data system (Medidata Rave). This data will be completed on an ongoing basis during the study. Data will be entered into electronic data systems by authorized individuals. Corrections to electronic data systems will be tracked electronically (password protected or through an audit trail) with time, date, individual making the correction, and what was changed.

13.3 Types of Data

Source documents include, but are not limited to, the subject's medical records, laboratory reports, ECG tracings, x-rays, radiologist's reports, subject's diaries, biopsy reports, ultrasound photographs, progress notes, pharmacy records, and any other similar reports or records of procedures performed during the subject's participation in the study.

13.4 Source Documents and Access to Source Data/Documents

Source documents include all recordings of observations or notations of clinical activities, and all reports and records necessary for the evaluation and reconstruction of the clinical trial. Data from Medidata Rave will be collected directly from subjects during study visits and telephone calls, or will be abstracted from subjects' medical records. The subject's medical record must record his/her participation in the clinical trial and, after unblinding, study treatment/vaccination (with doses and frequency) or other medical interventions or treatments administered, as well as any adverse reactions experienced during the trial.

13.5 Record Retention

The Investigator is responsible for retaining all essential documents listed in the ICH Good Clinical Practice Guideline. All essential documentation for all study subjects are to be maintained by the Investigators in a secure storage facility for a minimum of three years. The FDA requires study records to be retained for up to two years after marketing approval or disapproval (21 CFR 312.62), or until at least two years have elapsed since the formal discontinuation of clinical development of the investigational agent for a specific indication. These records are also to be maintained in compliance with IRB, state, and federal medical

records retention requirements, whichever is longest. All stored records are to be kept confidential to the extent required by federal, state, and local law.

